#### Relationship between spontaneous blink rate and striatal dopamine

The hypothesized relationship between spontaneous eye blink rate and striatal DA has been around for the last several decades. Experimental evidence supporting this hypothesis exists almost exclusively in animal research and in patient populations despite being used as an established measure during tasks. Using pharmacological and neurotoxic manipulations of the DA system in monkeys, a strong case has been made for the role of striatal DA in moderating spontaneous blink rates with striatal DA levels being positively correlated with spontaneous blink rates. This link has been made using direct, and indirect DA agonists in Cynomolgus monkeys, and was further refined by isolating the caudate as a potential key source of this link using the dopaminergic neurotoxin MPTP in monkeys (*cercopithecus aethiops sabaeus*). By using the well established dopaminergic abnormalities in schizophrenia and Parkinson's Disease, research in these patient populations have indicated that these DA abnormalities seem to be inducing the expected changes based on each disease's dopamine profile consistent with the animal literature. This work seeks to extend past patient and animal research by being the first to directly compare and experimentally manipulate the relationship between striatal dopamine binding and spontaneous blink rate.

## **8. PROGRESS REPORT**

To date a total of 47 participants have been enrolled into the study. We have successfully completed a total of 46 [C]DASB (in 18 CW, 11 REC AN, 10 REC AN-BN, 7 REC BN) and a total 47 [C]raclopride scans (in 19 CW, 11 REC AN, 10 REC AN-BN, 7 REC BN).

## **9. RESEARCH DESIGN AND METHODS**

### Screening and Assessments Prior to Imaging Studies:

Once the written consent has been obtained, subjects will complete screening interviews (for Axis I and II diagnoses, including ED subtype diagnosis), a physical examination (15-20 min), and laboratory tests, e.g., EKG,

VS, hemoglobin, hematocrit, total leukocyte with differential, plasma electrolytes, liver and thyroid function (T3, T4 and TSH levels), urinalysis, toxicology and confirmation of toxicology results (if required), cortisol levels, estradiol levels and pregnancy test prior to entering the study as previously described. The measures used in this study include the Structured Clinical Interview for DSM-IV Axis I Disorders (SCID-I) to assess the lifetime prevalence of Axis I psychiatric disorders, a modified version of Module H of SCID-I to assess lifetime diagnoses of EDs and subtypes and the Yale-Brown Obsessive Compulsive Scale for the assessment of OCD symptoms. Subjects will self-report ED symptoms, depression, anxiety, impulsivity, perfectionism, and temperament. To reduce confounding influences, we will exclude ED subjects who, in the past 3 months, have been on psychoactive medication or met criteria for substance abuse/dependence, major depression, or an incapacitating anxiety disorder.

Subjects will also complete behavior self-ratings including assessments of personality, mood, depression, anxiety, impulsivity and other behaviors relevant to eating disorders (See Table 2 for complete listing). These assessments will be sent to their home prior to scheduling them for an interview. The dominant hand will be assessed by the Edinburgh Inventory for analysis of handedness.

**Table 2: Interviews and self-assessments**

Name	Abbreviation	Area assessed	Minutes
Interviews:			
Mini-International Neuropsychiatric Interview	M.I.N.I. Plus	Axis I diagnoses	60
Module H of SCID I, Modified	Module H	ED diagnoses	30
Yale-Brown Obsessive Compulsive Scale	Y-BOCS	OCD	30
Yale-Brown-Cornell Eating Disorder Scale	YBC	ED symptoms	15
Set-shifting	SS	Inflexibility	5
Self-Assessments:			
Beck Depression Inventory	BDI	Depression	10
Spielberger State-Trait Anxiety Scale-Version Y	STAI-Y	State and trait anxiety	10
Eating Disorders Inventory -2	EDI-2	Core ED symptoms	15
Multi-dimensional Perfectionism Scale	MPS	Perfectionism	10
Barrett Impulsivity Scale	BIS	Impulse control	10
Temperament and Character Inventory	TCI	Personality and temperament	30
Sensation Seeking Scale	SSS	Sensation Seeking	15

**Study-Day Session Procedures:** Each study will be done during the early follicular phase (days 1 to 10) of the subject's menstrual cycle. Subjects will arrive the day before the study and stay overnight at the Clinical and Translational Research Institute (CTRI) at UCSD. On the day of the study, they will be awakened at 6:00 A.M. by the research staff. After a light breakfast, they will be transported by taxi to the Keck Center for Functional Magnetic Resonance Imaging on the UCSD campus at 7:00 A.M. After the acquisition of the structural MRI, which will be completed in about 30 minutes, the subjects will be transported again by taxi to the UCSD NeuroPET Center. The subjects will be informed of all of the procedures that will be performed and the information that will be obtained. The subject confirmation will be made via the signed copy of the written informed consent and then an intravenous catheter will be placed in either the left or right antecubital vein. After insertion of an intravenous catheter in a forearm vein, and a 20 minute transmission scan, a PET scan will be acquired following a slow bolus administration (over 20 sec) of 15 mCi of high-specific activity [C]DASB. Emission data will be collected in 3D mode for 100 minutes using a standard PET protocol as previously

described. At the completion of the scan, the IV lines will be removed. An EKG, vital signs, mental status and physical exam will be performed and evaluated by the study physician prior to the subject's discharge from the PET suite.

On the following day, the second day of the study, they will be awakened at 7:00 A.M. by the research staff. After a light breakfast, they will be transported again by taxi to the UCSD NeuroPET Center. After insertion of another intravenous catheter and following another transmission scan, the first PET scan will be acquired following a slow IV bolus administration (over 20 sec) of 10 mCi of high-specific activity [C]raclopride. Emission data will be collected in 3D mode for 60 minutes using a standard PET protocol as previously described. The participant will then be able to rest outside the scanner and will receive a physical exam, mental status exam, EKG, and vital signs measurement. The IV will stay in place. Thirty minutes following the first scan with [C]raclopride, the participant will receive 0.5 mg x kg of oral AMPH. Blood pressure and heart rate will be recorded every two minutes for the first 15 minutes, every five minutes for the next 30 minutes, and then every 15 minutes (up to at least 180 min). The post-AMPH [C]raclopride scan will be performed 3 hours after the administration of AMPH. Assessment of behavioral responses will be conducted before and after PET scans. The participants will complete a symptom-rating visual analog scale (VAS) pre-baseline PET, pre-AMPH, and then at 30 minute intervals a questionnaire assessing several states: "happy," "anxious," "energetic," "restless." To assess study participants' mood states and fluctuations, we will utilize, at the same intervals, the short version of Profile of Mood States (POMS-B). The POMS is a useful measure of mood states and their fluctuations and is appropriate for both research and therapy. It is a factor-analytically derived self-report inventory that measures six identifiable mood or affective states: tension-anxiety; depression-dejection; anger-hostility; vigor-activity; fatigue-inertia; and confusion-bewilderment. For more than 30 years, the POMS assessment has provided a valid and reliable measure of affective mood states. The short version, POMS Brief, developed in 1989, has a total of 30-items with five on each of the six POMS factors. Like the longer version, the POMS-B has excellent internal consistency. Items are rated on a 5-point scale (not at all, a little, moderately, quite a bit, extremely) and they only take five minutes to complete. The items are easy for patients to understand, allowing them to quickly and accurately complete the assessment. The basic stop signal task will be done after the 1st [C]raclopride (at baseline) and then shortly after the 2nd [C]raclopride (post-AMPH) scan. The study will be completed by approximately late afternoon. At the completion of the second scan, the IV lines will be removed. An EKG, vital signs, mental status and physical exam will be performed and evaluated by the study physician prior to the subject's discharge from the PET suite. The subject will be served a cafeteria-style assortment of lunch foods following the [C]DASB scan on Day 1 and the post-AMPH [C]raclopride scan on Day 2. The uneaten food will be weighed after completion of the meal and the total calories consumed will be recorded.

MRI Protocol: All participants will undergo an MRI procedure for anatomical localization of ROIs. Only one MRI will be done per participant. A single MRI study will be performed at the UCSD Keck Center for Functional MRI using a GE Excite HDx 3.0 Tesla scanner as described in our parent grant. The registered MRI will be used as an individualized anatomic map for the selection of ROIs used in the analysis of the PET data (see section Neuroimage Analysis).

Radiochemistry of [C]raclopride and [C]DASB:

[C]raclopride will be prepared at the UCSD Center For Molecular Imaging, PET Radiochemistry Laboratory. Radioactive [C]CO2 will be produced by the N(p, α)C nuclear reaction at the CTI RDS 111 cyclotron operated by PETNET. The [C]CO2 will be converted into [C]CH3I in GE Tracerlab FX MeI box sequentially swept into a silver triflate oven to produce [C]methyl triflate. O-desmethyleraclopride tetrabutylammonium precursor that is reacted using the HPLC loop injection port procedure. Then, the contents of the loop will be quantitatively injected into a semi preparative liquid chromatography column. The [C]raclopride fraction will be isolated, passed through a 0.22 μm sterile Millex-GV membrane filter, and collected in a 30 mL sterile vial already containing 15 mL of 0.9% sterile saline. Quality Assurance will be

performed as recommended by the FDA. For [C]raclopride the radiochemical yield is 30-40% at the end of synthesis. The total synthesis time will be 40± 5 min. The specific activity at the end of the analysis is 1500 Ci/mmol to 4000 Ci/mmol. The studies are carried out under IND 74,250.

[C]DASB will be prepared at the UCSD Center For Molecular Imaging, PET Radiochemistry Laboratory. Radioactive [C]CO2 will be produced by the N(p, α)C nuclear reaction at the CTI RDS 111 cyclotron operated by PETNET. The [C]CO2 will be converted into [C]CH3I desmethyl-DASB precursor that is reacted using the loop injection port procedure. Then, the contents of the HPLC loop will be quantitatively injected into a semi preparative liquid chromatography column. The product will be transferred into a flask containing a multiple volume (10x with respect to the product peak volume) of HPLC water. After that the aqueous solution is pushed through a solid phase extraction cartridge containing C-18 (usually WATERS SepPak light C-18 cartridge). The product is retarded on the C-18 cartridge. The cartridge is washed with 10 ml sterile water followed by product extraction with 1 ml USP EtOH transferred into a sterile product vial already containing 19 ml isotonic saline using a 22 μm sterile Millex-FG membrane filter. Quality Assurance will be performed as recommended by the FDA. The total synthesis time will be 50± 5 min. The average specific activity at the end of the analysis has averaged 1000 to 5000 Ci/mmol. The studies are carried out under IND 74, 254 for [C]DASB.

Dextroamphetamine sulfate (oral) is the dextro isomer of the compound d,l-AMPH sulphate. It is an FDA approved drug available for the treatment of narcolepsy and attention deficit hyperactivity disorder (maximum approved total daily dose of 5-60 mg). It is manufactured and marketed under the commercial name Dexedrine by GlaxoSmithKline pharmaceuticals. As dexedrine is available as an orange, triangular, scored tablet in 5 mg, 10 mg and 15 mg strengths, it will be dispensed by the pharmacy as nearly as it can be approximated to 0.5 mg/kg (in 2.5 mg increments). For example a subject who weighs 50 kg or 54 kg will receive 25 mg of AMPH, while a subject who weighs 55 kg will receive 27.5 mg of AMPH. The use of AMPH in this study will be in an off-label manner. The pharmacokinetics and behavioral effects of oral dextroamphetamine peaks at 3h. Several other groups have successfully used oral AMPH in the dose range of 0.43-0.5 mg/kg in PET imaging studies.

PET scan protocol: The PET imaging will be done at the UCSD NeuroPET Center using a HR+ PET scanner under the supervision of Drs. [name] and [name]. An intravenous catheter will be placed in a forearm vein for radiopharmaceutical infusion (this protocol will not involve arterial catheterization) and collection of blood samples. The subject's head will be positioned and immobilized using a vacuum bead padding to decrease head movement during the scan. A 20 minute transmission scan, using rotating rods of Ge-68/Ga-68, will be obtained for attenuation correction of the emission scan(s). On the first day of the study, after the transmission scan, a PET scan will be acquired following a slow bolus administration (over 20 sec) of 15 mCi of high-specific activity [C]DASB. Emission data will be collected in 3D mode for 100 minutes using a standard PET protocol as previously described. At the completion of the scan, the IV line will be removed. On the next day, following another transmission scan, the first PET scan will be acquired following a slow IV bolus administration (over 20 sec) of 10 mCi of high-specific activity [C]raclopride. Emission data will be collected in 3D mode for 60 minutes using a standard PET protocol as previously described. Blood pressure and heart rate will be recorded every two minutes for the first 15 minutes, every five minutes for the next 30 minutes, and then every 15 minutes until the subject is placed in the PET scanner (up to at least 180 min). The second [C]raclopride scan will be done 3 hours post AMPH and will require a second PET transmission scan. During the waiting period (post AMPH), the participant will be asked to perform a few structured tasks and rating scales such as the Visual Analog Scale (VAS) and Profile of Mood Scale (POMS) to contrast with baseline. Approximately 5 mL of venous blood will be drawn at 0 and 30 min relative to the second [C]raclopride scan to measure plasma AMPH levels. Following each PET scan, an EKG, vital signs, mental status and physical exam will be performed and evaluated by the study physician prior to the participant's discharge from the UCSD PET center and the IV line will be removed.

Stop Signal Task: The basic stop signal task will be done after the 1st [C]raclopride (at baseline) and then shortly after the 2nd [C]raclopride (post-AMPH) scan. The test-retest reliability of the task is high. The task has been implemented in Matlab and Psychtoolbox 3, and can be run in 15 minutes, including practice. SSRT, the main dependent measure, will be computed using an approach that is optimal for treating between-group differences.

## Neuroimage Analysis

MRI-Based Region of Interest (ROI) Definition for analysis of PET Data. PET and MRI image sets are aligned using PET/MRI fusion software (IDL, ITT Visual Information Solutions). ROIs are defined on MRI images across all MRI slices passing through those structures using an ROI drawing tool (imagetool) by trained tracers (blind to the diagnosis) with established reliability. For the [C]raclopride and [C]DASB studies ROIs will include the three functional sub-divisions (limbic, associative and motor) of the striatum as outlined by Martinez *et al.*. The limbic striatum comprises the AVS; the associative striatum comprises the pre-commissural DC, precommissural dorsal putamen and postcommissural DC; the motor striatum comprises the post commissural dorsal putamen. For the [C]DASB studies, as outlined by Frankle *et al.*, The subcortical regions include thalamus, insula, midbrain, medial temporal lobe (a spatially weighted average of 5 limbic structures, the uncus, amygdala, entorhinal cortex, parahippocampal gyrus, and hippocampus). The neocortical ROIs are as follows: DLPFC, medial PFC, OFC, ACC, temporal and occipital cortex. The cerebellum will be used as reference region for both studies. A different set of ROIs are routinely utilized for fMRI studies. As a result, we will define a second ROI set that will be applied to the PET BPND maps and enable us to perform the integrative analyses to relate the PET and fMRI data in exploratory AIM 4.

Anatomically constrained functional regions of interest for fMRI analyses. One of our co-investigators, [name], in collaboration with his colleagues, has developed methods for reconstructing the cortical sheet based upon routine 3D T1-weighted MRI volumes. FreeSurfer not only allows for the accurate measurement of cortical thickness, it also provides a method for parcellation of the cortical surface, where each location on the surface is assigned a neuroanatomical label based upon probabilistic information estimated from a manually labeled training set. The ROIs that will also be used for fMRI analysis include: bilateral caudate, ventral striatum, medial PFC, ACC, DLPFC, medial OFC, inferior frontal gyrus, inferior parietal cortex, and AI.

Analysis of PET Data: The “PET” ROIs will be applied to the dynamic [C]raclopride and [C]DASB images to obtain decay-corrected, time-radioactivity curves using a calibrated phantom standard to convert tomographic counts to  $\mu\text{Ci/ml}$  for each time point. Analysis of the PET data for both [C]raclopride and [C]DASB will be performed using both the simplified reference tissue and graphical reference tissue methods with the cerebellum as reference region for non-displaceable uptake. Both of these reference tissue methods have been shown to be appropriate models for quantifying [C]raclopride and [C]DASB binding in humans without an arterial input function. The outcome measure derived from these analyses is BPND. BPND (unitless) is equal of  $f_{\text{ND}}B_{\text{avail}}/K_{\text{D}}$  where  $B_{\text{avail}}$  is the concentration of receptors available for radioligand binding *in vivo* (not bound to endogenous ligand),  $K_{\text{D}}$  is inversely related to the *in vivo* affinity of radioligand for receptor binding and  $f_{\text{ND}}$  is the fraction of radiotracer freely dissolved in tissue water (i.e. free fraction) in the non-displaceable compartment. We will also generate parametric BPND maps that will be spatially normalized to the MR data set and the “fMRI” ROIs will then be applied to sample the normalized PET BPND maps.

FC analysis across regions. We will explore functional inter-relationships in AI, OFC, striatum, and ventral and dorsal putamen by combining information from both fMRI and PET data. Initial analyses will assess for outliers and distributions of fMRI and PET data times series to ensure modeling assumptions are met. Outliers will be Winsorized; non-normality will be handled via appropriate transformations. Missing data will be multiply imputed. FC of activation in these regions in response to sucrose stimulus will be assessed on an individual subject-level basis via partial cross-spectrum of BOLD activation time series. The partial cross

spectrum will be used to estimate the normalized partial mutual information, an overall measure of the linear and nonlinear FC between pairs of regions controlling for activations in the remaining regions. The stimulus waveform will also be entered as a separate time series in this model to control for non-stationarity in activation of regional BOLD time series due to stimulus. The resulting FC estimates will then be entered into a random effects model with clustering of responses by subject; subject-level PET 5-HT/DA function in these same regions will be entered along with group membership (REC AN, REC AN-BN, REC BN, and CW). This random effects model will be used to test for whether any group differences in FC in this network are (partially) explained by subject differences in 5-HT and/or DA function. The methods implemented in the FC toolbox in MATLAB (Version 7.6) will be adapted to perform these analyses.

Exploratory analyses of PET and fMRI data relationships. Relationships between the PET BPND and  $\Delta$  in BPND values and the fMRI results will be explored with supplemental statistical analyses, performed across subjects. First, task-specific BOLD fMRI activation will be related to a specific PET BPND value following the methods of Fisher et al. (2009). A partial least squares (PLS) multivariate analysis will be applied to relate regional results and/or voxel level contrast maps. PLS is a non-parametric dimension reduction method that will utilize 2 blocks of manifest variables (X and Y) that can be statistical contrasts, covariates or neuroimaging data. The inter-block covariance matrix RYX between X and Y is determined and primary outcomes are scores that represent the elements of block-X and block-Y that are most correlated. PLS can be applied to relate fMRI single-subject ROI results to PET BPND maps or relate a difference map for a fMRI BOLD contrast to a difference map for a PET BPND contrast between groups.

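### The exploratory Aim 4 connectivity network lists striatum beside ventral and dorsal putamen; if striatum is a composite containing them, partial connectivity conditions a region on its own parts.

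*Combined protocol and SAP*

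**What the plan says.** Section 9, Neuroimage Analysis, paragraph on FC analysis across regions, gives the network: "We will explore functional inter-relationships in AI, OFC, striatum, and ventral and dorsal putamen by combining information from both fMRI and PET data". Connectivity is "assessed on an individual subject-level basis via partial cross-spectrum of BOLD activation time series", and the resulting partial mutual information is "an overall measure of the linear and nonlinear FC between pairs of regions controlling for activations in the remaining regions". These values become the responses in a random effects model with diagnostic group and the PET measures.

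The same section has two region schemes.

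- **PET scheme (raclopride and DASB).** The limbic part is the AVS alone. The next part is set out as "the associative striatum comprises the pre-commissural DC, precommissural dorsal putamen and postcommissural DC", and the last one is given by the words "the motor striatum comprises the post commissural dorsal putamen". Both parts of the dorsal putamen are therefore striatum. Ventral putamen is not assigned by name, although the Aim 2A analysis text lists it among the regions for raclopride binding.
- **fMRI scheme.** "The ROIs that will also be used for fMRI analysis include: bilateral caudate, ventral striatum, medial PFC, ACC, DLPFC, medial OFC", followed by inferior frontal gyrus, inferior parietal cortex and anterior insula. It has no putamen and no whole striatum.

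No sentence says which scheme supplies the striatum node, or that this node leaves out the putamen.

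**The concern.** A partial measure asks what two regions share once the other nodes are held fixed. That is meaningful when the nodes are distinct. If one node is an average that contains two others, fixing the average and one part forces the remaining parts to trade off against each other. The estimate then reflects the arithmetic of the average as well as the brain.

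Two of the ten pairs in a five-node network (striatum with each putamen region) would share signal directly. The ventral-dorsal putamen pair, and under some conditions the cortex-putamen pairs, would be altered by the conditioning. An induced negative dependence would also show as positive connectivity, because mutual information has no sign. The stake is where a result is placed: a true insula-caudate link could be reported partly as an insula-putamen link, and that value would then be related to serotonin and dopamine binding.

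**Working it through.** The plan gives no sample size, power or error rate for this analysis, so there is no figure to reproduce. The check is of the mechanism, using partial correlation as the Gaussian, single-frequency analogue of the partial cross-spectrum.

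**Inputs.** From the plan: the node list and the conditioning rule. Assumed, because the plan gives no values: the composite's weights, the noise and the correlations.

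**Set-up.** Let A be insula, C the striatum outside the putamen, V ventral putamen and D dorsal putamen, each with variance 1. Take C, V and D as independent, and A correlated ρ with C only. Let S = w_C·C + w_V·V + w_D·D + noise (variance σ²). Write a = w_V/w_C, b = w_D/w_C and τ² = 1 − ρ² + σ²/w_C². Given A, V and D, the quantity S/w_C has mean ρA + aV + bD and variance τ². Reading partial correlations off the inverse covariance gives:

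- S–V: a/√(τ² + a²)
- V–D: −ab/√[(τ² + a²)(τ² + b²)]
- A–V: −ρa/√[(τ² + ρ²)(τ² + a²)]
- partial mutual information: −½ ln(1 − r²)

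With disjoint nodes (C in place of S), all three true values in this set-up are 0.

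**Case 1: all regions independent (ρ = 0).**

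| Weights C/V/D | S–V | S–D | V–D |
|---|---|---|---|
| equal | 1/√2 = 0.71 | 0.71 | −1/2 = −0.50 |
| 0.5/0.2/0.3 | 0.4/√1.16 = 0.37 | 0.6/√1.36 = 0.51 | −0.24/√(1.16 × 1.36) = −0.19 |
| 0.6/0.2/0.2 | 0.32 | 0.32 | −0.10 |

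With equal weights and noise equal to 20% of the composite's variance, σ²/w_C² = 0.6 and τ² = 1.6, so V–D = −1/2.6 = −0.385. The noise-free −0.50 gives partial mutual information of −½ ln(0.75) = 0.144, reported as positive. In a simulation with an assumed 200 time points, 2,000 replicates and equal weights, V–D was falsely significant at the 5% level in 100% of replicates, against 4.75% with disjoint nodes. The A and OFC links stayed at 0 in this case.

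**Case 2: insula coupled to the rest of the striatum only.**

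- ρ = 0.4, equal weights, no noise: A–V = −0.4/√(1.00 × 1.84) = −0.295.
- ρ = 0.4, weights 0.5/0.2/0.3: A–V = −0.16/√(1.00 × 1.00) = −0.16; A–D = −0.24/√(1.00 × 1.20) = −0.22.
- ρ = 0.5, equal weights, noise SD 0.05: τ² = 0.75 + 0.0225 = 0.7725; A–V = −0.5/√(1.0225 × 1.7725) = −0.37.
- ρ = 0.5, equal weights, noise SD 0.3: τ² = 0.75 + 0.81 = 1.56; A–V = −0.5/√(1.81 × 2.56) = −0.23.
- ρ = 0.5, equal weights, subregions correlated 0.5 (numerical inversion): A–V = −0.27 to −0.09 over the same noise range.
- ρ = 0.5, weights 0.5/0.2/0.3, over both noise levels and both subregion correlations: A–V = −0.21 to −0.06; A–D = −0.28 to −0.10.

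The truth for A–V and A–D is 0 throughout, and disjoint nodes return 0.

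**Case 3: does it reach group differences?** With equal weights and no noise, A–V = −ρ/√(2 − ρ²). At ρ = 0.4 this is −0.295 (mutual information 0.045); at ρ = 0.5 it is −0.378 (0.077). The false link follows the true insula-striatum coupling. Two groups with the same coupling and signal structure get the same false value and no false difference. If their coupling differs, part of that difference appears at the putamen.

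**The case against.** The strongest reply is that the overlap is inferred. The subdivisions that place dorsal putamen in the striatum belong to the PET scheme, whereas connectivity is computed on BOLD series, for which the plan uses a different region set. No whole-striatum BOLD region is defined anywhere. Striatum may be shorthand for the listed caudate and ventral striatum, which would remove the dorsal putamen overlap. The fMRI list is introduced as what the regions include, so it need not be complete, and the fMRI data come from a separate project whose region specification is not in these documents.

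All of that stands, and it makes the point conditional. It does not remove it: the sentence that sets the network lists striatum beside two of its parts, and no text excludes them. Under the shorthand reading, ventral putamen could still overlap ventral striatum.

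Three stronger readings are tempting, and the documents do not support them.

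- **That the nodes are known to share voxels.** The BOLD nodes are not defined, so overlap follows from a plain reading of the list and is not established.
- **That every link with insula or orbitofrontal cortex is distorted.** Cortex-putamen links are affected only when the cortical region is truly coupled to the rest of the striatum. The insula-orbitofrontal link was unchanged in every scenario tried.
- **That the group comparison is biased.** That needs true coupling or signal structure to differ by group. Specific Aims does report opposite insula-striatal responses to sucrose in recovered AN and BN, which makes a difference plausible, but those are response levels and not coupling estimates.

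It is also fair that the sizes depend on assumed weights, and that static partial correlation stands in for the planned frequency-domain measure.

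**Conclusion.** The point holds in conditional form. If the node list is followed with striatum as a composite containing the putamen, the striatum-putamen values are inflated by shared signal (0.32 to 0.71 when the regions are truly independent). The ventral-dorsal putamen value is displaced (−0.10 to −0.50 in the noise-free cases where the truth is 0). False cortex-putamen links of roughly −0.1 to −0.4 appear when the cortical region is coupled to the rest of the striatum. These sizes are illustrative and rest on the assumed weights, noise and correlations; dilution by noise, unequal weights and correlated subregions together brought the smallest to −0.06.

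The likely harm is that a real effect is placed at the wrong striatal node. The analysis belongs to exploratory Aim 4, so the aims with stated power (1, 2A, 2B and 2C) are untouched. The node list should be corrected before the connectivity values are computed, because as written it can yield links by construction.

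**What to change.** In the paragraph on FC analysis across regions, replace striatum with named BOLD nodes that do not overlap: the caudate and ventral striatum already in the fMRI list. If the putamen is wanted, add ventral and dorsal putamen to that list as separate, disjoint regions, and state that ventral putamen voxels are excluded from ventral striatum. Add one sentence saying that no voxel belongs to more than one node. In the scenarios tested, disjoint nodes returned the true value of 0 for the false putamen links.

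The cost is a revised region list and the matching masks. No new scans, participants or changes to the other aims are needed.
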